## 11.2 Data Analyses Plans

Primary Endpoint Analysis:

Phase 1b: DLT count and proportion will be reported. Type, grade and attribution will be described by body system in the first 10 DLT evaluable patients. Number of IL-2 cycles and doses and Nivolumab doses will be summarized.

Phase II: Overall response rate at 12 weeks will be reported with the sample size and proportion of evaluable patients and the corresponding 95% exact binomial confidence interval.

Secondary Endpoint Analyses:

Safety will be defined by frequency of drug-related grade 3-5 adverse events including adverse events of interest within the duration of protocol, specified therapy and an additional 60 days following the last dose with the combination of HD IL2 and nivolumab, as assessed by NCI's CTCAE version 4.0. Counts and frequencies will be reported by body system, type and grade. Cycles and of each drug and doses/cycle of IL-2 will be described using descriptive statistics.

Survival endpoints are 24-month Overall Survival (OS) and 24-month Progression-Free Survival (PFS) as assessed by RECIST 1.1 criteria in subjects treated with the combination. Product-limit estimates from Kaplan-Meier methods will be used to report the 24-month OS and PFS proportions with 95% confidence intervals. Kaplan-Meier figures will be produced.

Interim Analysis for efficacy: An interim analysis for efficacy is planned after 12 response evaluable patients have been enrolled (total in the phase I b/II portions). If 2 or less patients have a response at 12 weeks then the trial will terminate. .

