##### **2.3 Secondary Objectives**

- 2.4.1 To determine the safety of High Dose Interlukin-2 in combination with the immune checkpoint inhibitor Nivolumab in metastatic clear cell renal cell carcinoma.
- 2.4.2 To profile circulating T cell repertoire by flow cytometry before and during therapy.

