##### **Phase II portion:**

Primary Endpoint: Efficacy of the combination therapy will be determined by the overall response (ORR) rate/proportion with response including complete response rate/proportion as assessed by RECIST 1.1 criteria.

Secondary Endpoints:

Safety will be defined by the frequency of protocol specified therapy-related grade 3-5 adverse events including events of clinical interest for duration of protocol specified therapy and an additional 60 days beyond that, as assessed by NCI's CTCAE version 4.0.

Survival endpoints for efficacy are 24-month Overall Survival (OS) and 24-month Progression-Free Survival (PFS) in subjects treated with the combination by RECIST 1.1 criteria.

To descriptively characterize the circulating immune cell repertoire before and after start of combination therapy with High Dose Interlukin-2 in combination with the immune checkpoint inhibitor Nivolumab

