### 8.2 Adverse Event Reporting Requirements

Adverse event (AE) monitoring and reporting is a routine part of every clinical trial and is done to ensure the safety of subjects enrolled in the studies as well as those who will enroll in future studies using similar agents. Data on adverse events will be collected from the time of initial study treatment administration or intervention through 60 days after the last dose of **study treatment** (study treatment here refers to the two possible cycles of interleukin-2 and/or last dose of nivolumab up to 48 weeks of therapy, whichever is later). Any serious adverse event that occurs more than 60 days after the last study treatment and is considered related to the study treatment must also be reported. Serious Adverse Events (SAEs) will continue to be followed until:

- Resolution or the symptoms or signs that constitute the serious adverse event return to baseline;
- There is satisfactory explanation other than the study treatment or intervention for the changes observed; or
- Death.

The investigator is responsible for the detection, documentation, grading and assignment of attribution of events meeting the criteria and definition of an AE or SAE. The definitions of AEs and SAEs are given below. It is the responsibility of the principal investigator to ensure that all staff involved in the trial is familiar with the content of this section.

Any medical condition or laboratory abnormality with an onset date before initial study treatment administration or intervention is considered to be pre-existing in nature. Any known pre-existing conditions that are ongoing at time of study entry should be considered medical history.

All events meeting the criteria and definition of an AE or SAE, as defined in Section 8.3, occurring from the initial study treatment administration or intervention through 60 days following the last dose of the study treatment (study treatment here refers to the two possible cycles of interleukin-2 and/or last dose of nivolumab up to 48 weeks of therapy whichever is later) or study intervention must be recorded as an adverse event in the patient's source documents and on the CRF regardless of frequency, severity (grade) or assessed relationship to the study treatment or intervention.

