### 8.4.2 Attribution of the AE

The investigator or co-investigator is responsible for assignment of attribution.

Definite – The AE *is clearly related* to the study treatment/intervention.

Probable – The AE *is likely related* to the study treatment/intervention.

Possible – The AE *may be related* to the study treatment/intervention.

Unlikely – The AE *is doubtfully related* to the study treatment/intervention.

Unrelated – The AE *is clearly NOT related* to the study treatment/intervention.

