#### 11.1 Study Design/Study Endpoints/Sample Size and Accrual

For the phase 1b portion of the study: We will accrue an initial cohort of 3 patients who will be treated with sequential (rather than interspersed) treatment as follows: they will receive 2 cycles of HD-IL2 given in standard fashion (two 5-day cycles one week apart) followed by nivolumab starting the week after the second IL-2 cycle and continuing every 4 weeks as per standard nivolumab dosing. If 2 or more out of 3 of the first patients suffer a grade 3 or 4 immune related toxicity of interest (see 5.2.1) **within 28 days** from the first dose of nivolumab (**DLT period**) the study will stop. The 4th patient will not be enrolled until after the analysis of the 3 patient cohort is complete and submitted to the regulatory bodies.

If <2 patients suffer a grade 3 or 4 immune related toxicity in the cohort of 3 patients, the study will enroll 7 more patients treated with Nivolumab administered intravenously at 480 mg/dose over 60 minutes every 28 days, starting 1 to 3 weeks after the start date of the first cycle of IL2. We will monitor these patients **continuously** for immune mediated dose limiting toxicities **for 28 days** from the first dose of nivolumab (**DLT period**). Up to 10 total patients will be treated and observed for toxicity for 28 days from the first dose of Nivolumab in the phase 1b portion.

If, at any time during accrual to the phase 1 b portion, 6 patients or more have a grade 3 or 4 immune mediated event of interest (as described in section 5.2.1) we will pause the study and modify/discontinue the protocol in consultation with the site principal investigators and applicable regulatory authorities. If 5 or fewer patients experience grade 3 or 4 immune mediated toxicity of interest (see 5.2.1) during the toxicity window, then the study will continue to the phase II portion.

We choose to examine toxicity after 10 patients because if 6 patients or more are found to have a DLT then the 95% exact binomial confidence interval (26% - 88%) will be > 25% and be indicative that immune mediated toxicity with this regimen is too great.

Dose-Limiting Toxicity is defined as a grade 3 or 4 immune mediated event of interest (as listed and described in section 5.2.1). Please note: immune mediated events of interest do not include those that might occur during high dose IL-2 and are reversible.

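### The full-trial safety result counts only drug-related grade 3-5 adverse events, so it depends on investigator attribution and leaves out grade 2 toxicities that stop nivolumab

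*Combined protocol and SAP*

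**What the plan says.** The phase II secondary objective in section 2.3 is "To determine the safety of High Dose Interlukin-2 in combination with the immune checkpoint inhibitor Nivolumab". Section 11.2 turns it into a result: "Safety will be defined by frequency of drug-related grade 3-5 adverse events including adverse events of interest within the duration of protocol", plus 60 days, with counts by body system, type and grade. Study Endpoints (phase II portion) has nearly the same definition: "Safety will be defined by the frequency of protocol specified therapy-related grade 3-5 adverse events including events of clinical interest".

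Data collection is wider. Under section 8.2, AEs through 60 days after the last dose are recorded "on the CRF regardless of frequency, severity (grade) or assessed relationship to the study treatment or intervention". On relatedness, section 8.4.2 says "The investigator or co-investigator is responsible for assignment of attribution", using five categories from definite to unrelated.

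For phase Ib, section 11.2 reports the DLT count and proportion and continues: "Type, grade and attribution will be described by body system in the first 10 DLT evaluable patients". Section 11.1 sets the grade for a DLT: "Dose-Limiting Toxicity is defined as a grade 3 or 4 immune mediated event of interest".

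**The concern.** The result meant to describe the safety of a new combination is narrower than the data collected, in two ways.

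The first is attribution. Whether a grade 3-5 event counts depends on a judgement by the treating team, who know that every patient receives both drugs. There is no control arm against which to check that judgement.

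The second is grade. The protocol treats many grade 2 toxicities as serious enough to interrupt nivolumab, and some as reasons to give systemic steroids. A summary that starts at grade 3 need not show them. The safety summary could then look more favourable than the database behind it, and a reader of the results could not tell.

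**Working it through.** The check is a comparison of sections. The plan states no figure on this point to reproduce.

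**1. What else could report AEs for the full trial?**
- Section 7.2 names the population (at least one dose of study drug) but no grade, attribution or table.
- Section 8.6 sends expected and unrelated AEs to annual data submission.
- Section 12.0 sends site safety reports to the DSMC.
- The exposure summaries in 11.2 count cycles and doses, not reasons for stopping.

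None of these specifies a results table.

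**2. Attribution.** Section 11.2 does not say which of the five categories count as drug-related. Section 8.5 groups definite, probable and possible for SAE reporting. With that grouping, events called unlikely or unrelated drop out. This holds however the rest of the definition is read.

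**3. Grade 2 toxicity.** During the nivolumab-only period, section 5.2 holds nivolumab for any non-hematologic toxicity of grade 2 or higher, and discontinues it if there is no improvement to grade 1 or better within 6 weeks of the prior dose. The 5.2.1 tables add these grade 2 actions:
- pneumonitis and hepatic events: delay nivolumab and give steroids;
- renal events: delay or discontinue, with steroids;
- diarrhea or colitis: hold, with steroids if symptoms last more than 7 days;
- neurological events: delay, with steroids to be considered.

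Some of these tables allow nivolumab to resume if the event improves within 12 weeks. The point does not depend on which time limit governs.

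**4. The clause on events of interest.** It can name a subset of the related grade 3-5 events, or add such events at any grade. Section 11.2 and Study Endpoints use slightly different terms, and neither cites 5.2.1.

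| Event, recorded on the CRF | Subset reading | Any-grade reading |
|---|---|---|
| Related, grade 3-5 | shown | shown |
| Grade 3-5, not an event of interest, called unlikely or unrelated | not shown | not shown |
| Related, grade 2, in 5.2.1 | not shown | shown |
| Related, grade 2, outside 5.2.1 (for example fatigue), nivolumab held | not shown | not shown |

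**5. Does phase Ib recover them?** The sentence on type, grade and attribution follows the DLT count, so it may describe only DLTs, which are grade 3 or 4. Read broadly, it covers 10 patients: 10/23 = 43% of evaluable patients at full accrual, or 10/12 = 83% if the trial stops after stage 1.

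**6. Does the range below grade 3 matter?** Table 1 of the protocol, for nivolumab alone, gives treatment-related events in 319 of 406 patients at any grade and in 76 at grade 3 or 4. The difference is 319 − 76 = 243, and 243/406 = 60%. For pneumonitis the counts are 16 and 6. The table does not separate grade 2 and is for monotherapy, so it supplies no rate for this regimen. It shows only that much related toxicity lies below grade 3.

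**The case against.** The strongest reply is that related grade 3-5 events are a sound choice of endpoint. The protocol's nivolumab benchmark uses almost the same filter: 19% of patients (76/406) with grade 3 or 4 treatment-related events. An all-cause count in a single-arm trial mixes in disease and background events. This stands, and it is why the related summary should stay. It does not argue against a second table beside it.

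The any-grade reading of the clause also has real support. On the subset reading the words add nothing to the count. Section 5.2.1 is headed as events of interest and its tables begin at grade 1. The DLT definition states a grade when one is meant. A reader might infer that grade 2 immune events will certainly be lost. The documents do not support that, because on the any-grade reading the 5.2.1 events are kept. But the wording leaves the choice open, and grade 2 toxicities outside 5.2.1 are missed either way.

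The attribution filter is not extreme. If 8.5 is followed, possible counts as related, and section 5.2 manages unclear toxicities before the second IL-2 cycle as possibly related to nivolumab. A reader might also infer that unrelated AEs go unreported. They do not: sections 8.2, 8.6 and 12.0 cover recording, annual submission and DSMC reports. What is missing is a planned results table.

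Finally, a reader might count related SAEs after 60 days as a further defect. Section 8.2 requires them to be reported, a fixed window is right for a frequency, and follow-up after therapy is by phone or similar contact every 12 weeks (section 6.3), so capture is passive. No change is needed there.

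**Conclusion.** The point holds as a cheap improvement to a descriptive analysis. Dependence on investigator attribution is certain from the text. The omission of grade 2 toxicities that hold or stop nivolumab is certain for events outside 5.2.1, and conditional on the subset reading for events inside it.

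No numerical size can be given. The documents contain no rate of grade 3-5 events judged unrelated and no rate of grade 2 holds under this combination. A reader might turn one reattributed patient into a shift of 1/23 = 4.3 percentage points, but 11.2 reports by body system, type and grade and specifies no overall patient proportion to shift. Nor do the documents show that attribution would in fact be biased; they show only that the planned result could not reveal it. The two-stage response rule, the DLT rule, the sample size and the power are untouched.

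The conclusion assumes that the 8.5 grouping defines drug-related, and that no fuller AE tables are planned outside these documents.

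**What to change.** In section 11.2 and Study Endpoints, keep the frequency of related grade 3-5 AEs as the safety endpoint, and add:

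1. One table of all AEs by worst grade, regardless of attribution, in all patients who received at least one dose (the section 7.2 population).
2. A sentence stating that adverse events of interest are the section 5.2.1 events at any grade, tabulated by grade with resulting nivolumab holds or discontinuations where these are recorded.

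The AE data for both are already required on the CRF. The cost is a short wording change and a little more analysis work. The safety summary will look less favourable and will include disease and background events, so the all-cause table should be labelled as such and read beside the related summary.

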#### **Analyses for correlative endpoints**

Flow Cytometry to profile circulating T cell repertoire including Tregs (CD4+/CD25+/FoxP3+) will be described graphically for pre-therapy and post-therapy.

All study information should be recorded in an appropriate source document (e.g. clinic chart).

#### Immunogenicity Analysis:

Immunogenicity results will be analyzed descriptively by summarizing the number and percentage of patients who develop detectable ADAs against nivolumab.

The immunogenicity titer and presence of neutralizing ADAs will be reported for samples confirmed positive for the presence of ADAs. The effect of immunogenicity on efficacy, and safety will be evaluated, if the data allow.

## **12.0 DATA AND SAFETY MONITORING**

- The Data and Safety Monitoring Committee (DSMC) of The University of Michigan Rogel Cancer Center is the DSMC for this study. This committee is responsible for monitoring the safety and data integrity of the trial. The committee will meet monthly (during the phase Ib portion) or quarterly (during the phase II portion).
- **Until the phase Ib portion is completed i.e. the first 10 patients have been treated and monitored for 28 days from the first dose of nivolumab, a biweekly phone call/webinar involving site Principal Investigators/Sub-investigator(s) from each site and relevant research staff at each site will be conducted to exchange information about toxicity/safety, subject clinical course and discern trends if any. The site investigators are highly experienced in the administration of HD IL2 and also, with nivolumab therapy.**
- At each site the study team is required to meet monthly (during the phase Ib portion) or quarterly (during the phase II portion) to discuss matters related to:
  - >Enrollment rate relative to expectations, characteristics of participants
  - >Safety of study participants (Serious Adverse Event & Adverse Event reporting)
  - >Adherence to protocol (protocol deviations)
  - >Completeness, validity and integrity of study data
  - >Retention of study participants
- These meetings are to be documented by the site data manager or study coordinator using the Protocol Specific Data and Safety Monitoring Report (DSMR), signed by the site principal investigator or co-investigator. Each site is required to submit the completed DSMR to the Multi-Site Coordinator at the University of Michigan Coordinating Center on a monthly (during

the phase Ib portion) or quarterly (during the phase II portion) basis together with other pertinent documents.

- Similarly, protocol deviations are to be documented using the Coordinating Center Deviation specified form and requires the signatures of both the sites data manager or study coordinator and the site principal investigator or co-investigator. These reports are to be sent to the University of Michigan Coordinating Center within 7 calendar days of awareness of the event and on a monthly (during the phase Ib portion) or quarterly (during the phase II portion) basis with the Protocol Specific Data and Safety Monitoring Report.
- The Coordinating Center is responsible for collating all the Data and Safety Monitoring Reports from all the participating sites, and providing the information to the Data and Safety Monitoring Committee.

### **13.0 QUALITY ASSURANCE AND AUDITS**

The Data and Safety Monitoring Committee can request a 'for cause' audit of the trial if the committee identifies a need for a more rigorous evaluation of study-related issues.

A regulatory authority (e.g. FDA) may also wish to conduct an inspection of the study, during its conduct or even after its completion. If an inspection has been requested by a regulatory authority, the site investigator must immediately inform the Coordinating Center that such a request has been made.

### **14.0 CLINICAL MONITORING PROCEDURES**

Clinical studies coordinated by The University of Michigan Rogel Cancer Center must be conducted in accordance with the ethical principles that are consistent with Good Clinical Practices (GCP) and in compliance with other applicable regulatory requirements.

This study will be monitored by a representative of the Coordinating Center. Monitoring visits will be made during the conduct of the study and at study close-out.

Prior to subject recruitment, a participating site will undergo site initiation meeting to be conducted by the Coordinating Center. This will be done as an actual site visit; teleconference, videoconference, or web-based meeting after the site's IRB approval and fully executed subcontract has been received by the Multi-Site Coordinator. The site's principal investigator and his study staff should make every effort in attending the site initiation meeting. Study-related questions or issues identified during the site initiation meeting will be followed-up by the appropriate Coordinating Center personnel until they have been answered and resolved.

Monitoring of this study will include both 'Centralized Monitoring', the review of source documents at the Coordinating Center and 'On-site Monitoring', an actual site visit. The first 'Centralized' visit should occur after the first subject enrolled completes first HD IL2 course (consisting of both weeks of IL2). The study site will send the de-identified source documents to the Coordinating Center for monitoring. 'Centralized' monitoring may be requested by the Coordinating Center if an amendment requires changes to the protocol procedures. The site will send in pertinent de-identified source documents, as defined by the Coordinating Center for monitoring.

The first annual 'On-site' monitoring visit should occur after the first five study participants are enrolled or twelve months after a study opens, whichever occurs first. The annual visit may be conducted as a 'Centralized' visit if less than three subjects have enrolled at the study site. The type of visit is at the discretion of the Coordinating Center. At a minimum, a routine monitoring visit will be done at least once a year, or once during the course of the study if the study duration is less than 12 months. The purpose of these visits is to verify:

- Adherence to the protocol
- Completeness and accuracy of study data and samples collected
- Proper storage, dispensing and inventory of study medication
- Compliance with regulations

During a monitoring visit to a site, access to relevant hospital and clinical records must be given by the site investigator to the Coordinating Center representative conducting the monitoring visit to verify consistency of data collected on the CRFs with the original source data. While most patient cases will be selected from patients accrued since the previous monitoring visit, any patient case has the potential for review. At least one or more unannounced cases will be reviewed, if the total accruals warrant selection of unannounced cases.

The Coordinating Center expects the relevant investigational staff to be available to facilitate the conduct of the visit, that source documents are available at the time of the visit, and that a suitable environment will be provided for review of study-related documents. Any issues identified during these visits will be communicated to the site and are expected to be resolved by the site in a timely manner. For review of study-related documents at the Coordinating Center, the site will be required to ship or fax documents to be reviewed.

Participating site will also undergo a site close-out upon completion, termination or cancellation of a study to ensure fulfillment of study obligations during the conduct of the study, and that the site Investigator is aware of his/her ongoing responsibilities. In general, a site close-out is conducted during a site visit; however, site close-out can occur without a site visit.

